8.0 RESPONSE CRITERIA

A 4-week period after the first infusion will constitute a course, which will be evaluated for critical toxicity.

Patients with measurable disease will be assessed by standard criteria to determine clinical response. Evaluations of tumor size will be performed pre-infusion and approx. every 2-3 months thereafter as per standard clinical care patient monitoring. All patients who receive multiTAA T cells and continue to be enrolled on the study will be evaluable for response. Patient long term overall and progression free survival will also be evaluated at 1 year and then annually for up to an additional 4 years (total of 5 years follow-up).

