9.0 STATISTICAL CONSIDERATIONS

9.1 Study Design Synopsis

This study is designed as a fixed-dose pilot study to evaluate the safety and feasibility (primary endpoints), and efficacy (tertiary endpoint) of up to 6 intravenous infusion of multiTAA-specific T cells in pancreas cancer patients with metastatic, locally advanced unresectable, or resectable disease.

In each disease group, the sample size is a maximum of 15 patients who receive at least one infusion of multiTAA-specific T cells. The total sample size of the study will be a maximum of 45.

We expect to enroll 15-20 patients per year and therefore expect the study to conclude accrual within the estimated period of 36 months.

Treatment-related serious adverse events (tSAE) are defined as grade III-IV CTCAE toxicity or grade 3-4 CRS toxicities that are determined to be related to T cells.

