9.2 Sample Size Determination and Trial Monitoring

In each of the disease groups, the primary goals are to study the safety of multiTAA-specific T cells and determine the feasibility of administering 6 infusions of cells.

To assess the safety of multiTAA-specific T cells: The sample size is 15 patients in each disease group, calculated based on the considerations as follows. To study whether there are excessive treatment-related serious adverse events (tSAE), a tSAE rate of 20% is considered excessive (corresponding to the alternative hypothesis), while a rate below 20% is considered acceptable. Based on our previous experience with T cell therapy, we anticipate at most 1.5% rate (corresponding to the null hypothesis). The monitoring rule is that if more than one tSAE is observed, then the treatment is considered unsafe and the accrual to the trial will be halted for that disease group.

Under the alternative hypothesis that the true tSAE rate is 20%, then the probability of observing more than one tSAE event out of 15 patients is 83.3% (statistical power for rejecting the null hypothesis, based on the exact binomial distribution). Under the null hypothesis that the true tSAE rate is 1.5%, the probability of observing more than one tSAE event out of 15 patients is only 2.08% (type I error for rejecting the null hypothesis, based on the binomial distribution).

There will be no formal interim analysis of safety but we will employ an ad hoc monitoring rule. The cumulative number of treatment-related serious adverse events will be counted for every 3 patients within each group. If there is more than 1 tSAE within a group, then the accrual to that group will be halted for excessive treatment-related serious adverse events. We will be looking at the data for at most 5 times for each group. Under the null hypothesis that the true tSAE rate is 1.5%, the probability of observing more than one tSAE event out of every 3, 6, 9, 12 and 15 patients is 0.07%, 0.32%, 0.76%, 1.34% and 2.08%, respectively. The overall type I error is thus controlled at 4.57% level.

The total sample size is 45. If there is any death deemed possibly or probably related to multiTAA T cell infusion, the study will halt patient accrual for the respective disease group, and the data will undergo a thorough internal review and the outcome discussed with the FDA.

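### Section 9.2 gives the tSAE rule an overall type I error of 4.57%, but the true value is 2.08%; since extra looks cost no error, the text should also say that accrual halts at the second tSAE

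*Combined protocol and SAP*

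**What the plan says.** All of this is in section 9.2 of the combined protocol and SAP unless another section is named.

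- **Limit, first statement.** "The monitoring rule is that if more than one tSAE is observed, then the treatment is considered unsafe", and accrual to that disease group then halts. No count schedule is attached.
- **Design figures.** Each group has 15 patients. The anticipated tSAE rate is at most 1.5% (null) and a rate of 20% is excessive (alternative). The stated power is 83.3% and the stated type I error at 15 patients is 2.08%.
- **Count schedule.** The plan has no formal interim safety analysis but an ad hoc rule: "The cumulative number of treatment-related serious adverse events will be counted for every 3 patients within each group". Then: "If there is more than 1 tSAE within a group, then the accrual to that group will be halted". And: "We will be looking at the data for at most 5 times for each group".
- **Overall error.** At a 1.5% rate, the chances of more than one tSAE by 3, 6, 9, 12 and 15 patients are given as 0.07%, 0.32%, 0.76%, 1.34% and 2.08%. The conclusion drawn is: "The overall type I error is thus controlled at 4.57% level".
- **What counts.** Section 9.1 defines a tSAE as "grade III-IV CTCAE toxicity or grade 3-4 CRS toxicities that are determined to be related to T cells".
- **Status of the rule.** Section 9.4 makes the guideline a trigger for FDA consultation, not automatic closure.

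**The concern.** Two things in this paragraph need attention, and they are linked.

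First, the section prints two type I errors for one rule: 2.08% for a single assessment at 15 patients, and 4.57% once the five counts are allowed for. A reader would conclude that the repeated counts more than double the chance of halting a safe group. They do not change it at all.

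Second, no sentence says what happens when the second tSAE falls between two counts. The halt could follow the event, or wait for the next multiple of three patients. The limit is there to restrict exposure, so waiting is worthwhile only if it buys something. If extra looks did cost error, batching could be defended on that ground. Once the error figure is corrected, that defence is gone.

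At stake are one misstated operating characteristic and, on the less protective reading, a patient or two enrolled in a group that has already reached its limit.

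**Working it through.** **Inputs, all from section 9.2.** n = 15 per group; limit of 2 or more tSAEs; rates p = 1.5% and p = 20%; counts at 3, 6, 9, 12 and 15 patients.

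**Step 1: reproduce the plan's figures.** The chance of 2 or more events in n patients is

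P(X ≥ 2) = 1 − (1 − p)^n − n·p·(1 − p)^(n−1).

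- n = 15, p = 0.20: 1 − 0.0352 − 0.1319 = 0.8329, the stated 83.3%.
- n = 15, p = 0.015: 1 − 0.79716 − 0.18209 = 0.02075, the stated 2.08%.
- n = 3, 6, 9, 12, 15 at p = 0.015: 0.067%, 0.324%, 0.755%, 1.344%, 2.075%. All five stated values are right.

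**Step 2: find where 4.57% comes from.** 0.07 + 0.32 + 0.76 + 1.34 + 2.08 = 4.57 (4.565% unrounded). It is the plain sum. Treating the looks as independent would give 4.495%, which does not match.

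**Step 3: compute the overall error.** The count in a group cannot fall and the limit is 2 at every look. A group over the limit at 3, 6, 9 or 12 patients would therefore also be over it at 15. The five events are nested, and the chance that any of them occurs is the chance of the last. Splitting by the look at which the limit is first crossed:

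| Look (patients) | p = 1.5% | p = 20% |
|---|---|---|
| 3 | 0.067% | 10.40% |
| 6 | 0.257% | 24.06% |
| 9 | 0.431% | 21.92% |
| 12 | 0.589% | 16.13% |
| 15 | 0.731% | 10.78% |
| Total | 2.075% | 83.29% |

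The totals equal the single-look values at 15 patients. A patient-by-patient calculation gives the same totals whether the rule is applied after every patient, after every third, or once at the end.

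As a check on the method, the same sum of cumulative probabilities at p = 20% is 10.4 + 34.5 + 56.4 + 72.5 + 83.3, about 257%. A sum that can exceed 100% is not a crossing probability.

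**Step 4: size the delay if the halt waited for a count.** Assume that patients enter one at a time, that each outcome is known before the next patient enters, and that each patient has at most one tSAE. Let T be the patient who brings the second tSAE:

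P(T = t) = (t − 1)·p²·(1 − p)^(t−2), t = 2, …, 15.

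The extra patients are 3·⌈T/3⌉ − T. At p = 20%:

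- Among groups reaching the limit, 0, 1 or 2 extra patients have probabilities 0.349, 0.342 and 0.309.
- Mean enrolment in those groups is 8.74 with waiting and 7.78 without, a difference of 0.96.
- Over all groups, including those that never reach the limit, it is 9.79 against 8.99, a difference of 0.80 (0.833 × 0.959 = 0.80).
- For true rates from 10% to 40%, the mean in groups reaching the limit stays between 0.93 and 0.96.

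**The case against.** **The 4.57% is a valid bound.** A sum of probabilities always bounds the chance that at least one of the events occurs, and the text speaks of control at that level. This stands as far as it goes: the true error is below 4.57%, and no limit, sample size or decision depends on the figure. But the sentence offers it as the overall type I error, and the exact value is already printed in the same section.

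**The ambiguity is thin.** Neither halt sentence is tied to a count, so a plain reading is that the halt follows the event and the counts are a periodic check. This also stands in large part. A reader might infer that section 9.2 contradicts itself, or that it obliges accrual to continue to the next count. The documents support neither: the count schedule can be read as the way the first statement is carried out, or as a check alongside it. What remains is that the schedule and the cap of five looks lean towards waiting, and nothing rules that out. Elsewhere the plan does tie a halt directly to an event, for example: "If there is any death deemed possibly or probably related to multiTAA T cell infusion, the study will halt patient accrual".

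**Timing may be settled elsewhere.** Section 12.3.4 sends serious adverse events to an SOP, and section 14.0 refers to monitoring plans that are not part of this document. They may fix the timing. One sentence in 9.2 would still remove the doubt.

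**The 0-to-2 range is conditional.** With six infusions, most of them a month apart, a second tSAE could surface just after the count at 6. Waiting until 9 would then add three patients. The range belongs to the assumptions in step 4, not to the plan. Lag in reporting would add patients under either reading and is a separate matter.

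**A wider criticism is tempting.** Section 8.0 says: "A 4-week period after the first infusion will constitute a course, which will be evaluated for critical toxicity". A reader might infer that later tSAEs fall outside the rule, or that the count lacks a defined window and denominator. The documents do not support making that a fault. Section 12.3.3 has adverse events collected until 8 weeks after the last dose, and sections 9.1 and 9.3.1 base the group size and the safety analysis on patients with at least one infusion.

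**Conclusion.** The stated overall type I error is wrong as an operating characteristic. It should be 2.08%; the 4.57% is a loose upper bound obtained by adding nested probabilities. This rests only on the plan's own binomial model, the cumulative counts and the fixed limit.

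The timing point is a clarification. Halting at the second tSAE and halting at the next count have the same power (83.3%) and the same false-halt probability (2.08%), so waiting gains nothing. On the waiting reading, and under the assumptions of step 4, the cost at a true 20% rate averages about one patient in a group that reaches the limit.

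Severity is minor. The rule leads to FDA consultation (9.4). Related deaths and toxicity-related surgical delays in Group C already halt accrual on the event (9.2, 9.4). A patient with related grade III-IV toxicity receives no further infusions (10.1.1), although that protects the affected patient and not the next one enrolled.

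**What to change.** In section 9.2:

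1. Replace the overall type I error of 4.57% with 2.08%, adding that the counts are cumulative against a fixed limit, so the number of looks does not change it.
2. State that accrual to a group halts as soon as its second tSAE is reported, whenever that happens, and that the counts every three patients are a backstop review.
3. Reword the five-look sentence so that it describes the scheduled reviews and does not limit when a halt can occur.

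The limit, the 15 patients per group, the power and the false-halt probability all stay as they are. The cost is an edit to one paragraph. The small operational burden is that grade III-IV events must be attributed to the T cells, or not, and reported promptly.

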9.4. Stopping Guidelines

Statistical monitoring of grade III-IV CTCAE toxicity or grade 3-4 CRS toxicities related to T cells is employed. Safety guideline and the rule for halting the accrual will be implemented separately for each cohort. The guidelines serve as a trigger for consultation with the FDA for additional review, and are not formal "stopping rules" that would mandate automatic closure. Additionally, after consultation with the FDA, the PI can stop the study early.

In Group C, it is extremely unlikely that patients who receive their first T cell infusions will not undergo surgical resection since all imaging studies and a clinical plan will be determined prior to infusion and it is unlikely that the T cells will cause inflammation precluding/delaying subsequent surgical resection. The accrual to Cohort C will be halted if any patient experiences a delay in subsequent surgical resection due to toxicity related to the T-cell infusion and this issue will be discussed with the FDA to develop a plan. The plan would be submitted to the DRC and IRB prior to resuming accrual to Cohort C.

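### The 4.57% overall type I error for the five-look tSAE rule in Section 9.2 is a sum of nested probabilities; under the plan's own binomial model it is 2.08% per disease group

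*Combined protocol and SAP*

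**What the plan says.** Section 9.2 of the combined protocol and SAP sets a null tSAE rate of 1.5%, an excessive rate of 20%, and 15 patients per disease group. More than one tSAE halts accrual to the group. For a single assessment at 15 patients it gives power of 83.3% and a probability of 2.08% under the null, which it labels "type I error for rejecting the null hypothesis, based on the binomial distribution".

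It then describes the repeated monitoring: "The cumulative number of treatment-related serious adverse events will be counted for every 3 patients within each group". The limit is again more than one. On the number of assessments: "We will be looking at the data for at most 5 times for each group". The null values are listed in one clause: "observing more than one tSAE event out of every 3, 6, 9, 12 and 15 patients is 0.07%, 0.32%, 0.76%, 1.34% and 2.08" (the last also in per cent). The next sentence draws the conclusion: "The overall type I error is thus controlled at 4.57% level".

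Two other halting triggers stand outside this calculation. One is in Section 9.2: "If there is any death deemed possibly or probably related to multiTAA T cell infusion, the study will halt patient accrual" for the group concerned. The other is in Section 9.4: "The accrual to Cohort C will be halted if any patient experiences a delay in subsequent surgical resection due to toxicity" related to the infusion. Section 9.4 also sets the status of the monitoring: "The guidelines serve as a trigger for consultation with the FDA for additional review".

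**The concern.** The section gives two type I errors for what is in effect one rule: 2.08% for a single assessment at 15 patients and 4.57% for five assessments. A reader would conclude that looking five times more than doubles the risk of wrongly halting a group. That would be the usual pattern if each look gave a fresh chance to cross. Here the count is cumulative and the limit is constant, so an early crossing is always still present at the last look. Adding the five probabilities counts the same crossing up to five times.

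Safety is a primary endpoint, and the overall type I error is a stated operating characteristic of its monitoring rule.

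**Working it through.** **Inputs (all from Section 9.2).** Null rate p0 = 0.015; alternative rate p1 = 0.20; 15 patients per group; looks at n = 3, 6, 9, 12 and 15; halt when the cumulative count is 2 or more.

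**Step 1: the plan's per-look values.** With at most one event per patient, the number of events X among n patients is binomial, and

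P(X ≥ 2) = 1 − (1 − p)^n − n·p·(1 − p)^(n−1).

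At n = 15 and p = 0.015: 1 − 0.985^15 − 15 × 0.015 × 0.985^14 = 1 − 0.79716 − 0.18209 = 0.02075.

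| Patients | Exact, p = 0.015 | Printed in 9.2 | First crossing at this look |
|---|---|---|---|
| 3 | 0.0668% | 0.07% | 0.0668% |
| 6 | 0.3242% | 0.32% | 0.2574% |
| 9 | 0.7552% | 0.76% | 0.4309% |
| 12 | 1.3438% | 1.34% | 0.5886% |
| 15 | 2.0752% | 2.08% | 0.7314% |

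All five printed values reproduce.

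**Step 2: where 4.57% comes from.** The printed values give 0.07 + 0.32 + 0.76 + 1.34 + 2.08 = 4.57. The unrounded values sum to 4.565%. Treating the looks as independent gives 4.50%, which does not match. The stated figure is the plain sum.

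**Step 3: the probability of crossing at any look.** Let A(n) be the event that the count is 2 or more by patient n. Because the count cannot fall, A(3) implies A(6), which implies A(9), and so on to A(15). The union of the five events is therefore A(15), and its probability is 2.0752%. The last column of the table gives the same result another way: it comes from a recursion that stops at the first look over the limit, and its entries add to 2.0752% before rounding. The total is the same with 1 or 15 looks. In a simulation of 4,000,000 groups at p = 0.015, 2.073% crossed at some look and 2.073% were over the limit at 15 patients.

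**Step 4: the same check under the alternative.** At p = 0.20 the per-look probabilities are 10.40%, 34.46%, 56.38%, 72.51% and 83.29%. Adding them, as was done under the null, gives about 257%, which cannot be a probability. The first-crossing probabilities are 10.40 + 24.06 + 21.92 + 16.13 + 10.78 = 83.29%, which agrees with the plan's 83.3%. The looks change neither error rate.

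**Step 5: dependence on one event per patient.** Suppose a patient with a tSAE has a further counted tSAE with probability q. The documents give no value, so q is an assumption. The rule then trips if two or more patients have an event, or if exactly one does and has a second:

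P(halt) = P(X ≥ 2) + q·P(X = 1) = 2.075% + 18.209% × q.

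| q | P(halt) under the null |
|---|---|
| 0 | 2.08% |
| 0.05 | 2.99% |
| 0.10 | 3.90% |
| 0.20 | 5.72% |

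The value 4.57% is reached at q = (4.57 − 2.075) / 18.209 = 0.137. A count that includes repeat events still cannot fall, so the looks add nothing in this case either.

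**The case against.** The best defence is the wording. To say that an error is controlled at a level is normally to state an upper bound, and a sum of tail probabilities is a valid one. Read that way, the sentence is loose but not false. This stands as far as it goes: under the binomial model the true error is indeed below 4.57%. But the section does not call the figure a bound. It derives it directly from the five listed values, gives it to two decimals and names it the overall type I error, although the exact value is already printed in the same section.

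A second objection is that the definition in Section 9.1 is by event, so one patient could contribute two, and 2.08% is then too low. Section 10.1.1 stops further treatment after related grade III-IV toxicity, which limits repeats but does not exclude several events in one episode. This is a fair reason to state the assumption beside the 2.08%. It does not support 4.57%, which was computed under the same one-event model.

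Third, nothing in the design turns on the figure. Section 9.2 calls the rule ad hoc, and Section 9.4 treats a crossing as grounds for consultation and not as automatic closure. That is correct and keeps the point minor. It does not make the number right.

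**Conclusion.** The concern holds. Under the plan's binomial model, with at most one counted tSAE per patient, the overall type I error of the five-look rule is 2.08% per disease group. The stated 4.57% is 2.2 times that (4.57 / 2.08). Power at a 20% rate is 83.3% with 1, 5 or 15 looks.

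The figure errs on the conservative side, since it overstates the risk of a false halt. The 2.08% covers the tSAE count only, within one group; it excludes the triggers for related death and for surgical delay in Group C. It also depends on the one-event assumption: the error would pass 4.57% only if the assumed probability of a further counted event exceeded about 0.14. Severity is minor.

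**What to change.** Replace the sentence on the overall type I error in Section 9.2 with:

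> Because the count is cumulative and the limit is the same at each look, the five looks do not inflate the type I error: under the binomial model used here, which assumes that each patient contributes at most one tSAE, the overall type I error of the tSAE rule is 2.08% per disease group (power 83.3%). This figure does not include the separate halting triggers for related death and Group C surgical delay.

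The clause on one tSAE per patient states what the calculation assumes; it does not set a counting rule. The last sentence is for clarity and could be dropped without affecting the correction. The five per-look probabilities can stay as printed.

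The cost is one replaced sentence. Sample size, limit, look schedule, counting and power are unchanged.

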9.3 Statistical Analysis

9.3.1 Safety Analysis of Toxicity and Adverse Event Data

All patients who receive at least one infusion of multiTAA-specific T cells will be included in the safety analysis. Patients will be monitored for clinical toxicity by the CTEP NCI Common Toxicity

Criteria Scale (Version 4.X, See Section 12.3) with the exception of CRS toxicities that are related to T cell infusions. CRS toxicities will be graded according to Appendix I.

Adverse event data and corresponding toxicity grades after T cell infusions and during long-term follow-up will be summarized in the form of tables. Incidence tables will be generated to summarize incidence of patients reporting at least one episode of each specific adverse event, incidence of adverse events causing withdrawal and incidence of serious adverse events. The total number of episodes for each event reported (Frequency Table), the severity and attribution to study therapy of each episode reported (Severity Table and Attribution Table) will also be calculated.

Listings of adverse events by patients will include the time to onset, the duration of each event, the severity of each event, and the relationship of the event to study therapy, whether it was a serious event, and whether it caused withdrawal. Safety data will be summarized for each patient group and for all treated patients.

9.3.2. Analysis of anti-tumor activity, progression-free and overall survival data

Although tumor response and survival are not the primary endpoint of this trial, we will summarize tumor response by calculating overall response rates along with exact 95% binomial confidence intervals. Response will be evaluated as described in section 8.4. The progression-free and overall survival of patients will be summarized using the Kaplan-Meier method. The analysis will be done for each patient group and for all treated patients. We will also explore the relationship between the patient baseline characteristics and response as well as PFS/OS based on eth logistic model and the Cox regression methods, respectively.

